## 9.6 Resilience in Pediatric Cancer Assessment (RPCA) Survey (all participants, including AYAs of run-in cohort):

Patient (and parent)-reported outcomes (PROs) will be measured with the Resilience in Pediatric Cancer Assessment (RPCA), a comprehensive survey comprised of age-appropriate validated instruments (**Table 5**). The RPCA was designed with AYA and parent stakeholders to capture patient-reported outcomes associated with resilience resources. We have successfully used it in several of our prior studies. The survey includes embedded validated instruments as well as standard demographics (age, sex, and race/ethnicity, education, income, number of children in the home). For the present study, we added an ad-hoc checklist querying the number and duration of discussions the family has had with health-care, psychosocial, or palliative care teams regarding concepts of prognosis, treatment goals, AYA hopes, worries, or concerns, and to what degree AYAs were involved in such discussions.

**Table 5. Resilience in Pediatric Cancer Assessment (RPCA) Instruments**

Objective	Concept	Instrument(s)	Source
Aim 1 (AYA Outcomes)	HRQOL (Primary Outcome)	PedsQL Generic Core and Cancer Modules (PedsQL) 20,21†‡	AYAs
	Anxiety/ Depression	Hospital Anxiety and Depression Scale (HADS) 22†‡	
	Symptom Burden	Memorial Symptom Assessment Scale (MSAS) 24†‡	
	Hope	Hope Scale 25†	
	Resilience	2-item Connor-Davidson Resilience Scale 	
		10-item Connor-Davidson Resilience Scale 94†	
Aim 2 (Parent Outcomes)	Anxiety	Generalized Anxiety Disorder Screener (GAD-7) 	Caregivers
	Depression	Patient Health Questionnaire (PHQ-8) 	
	HRQOL	Medical Outcomes Study Rand Short-Form 36 29‡	
	Family Experience	Family Experience Survey (HCAHPS) 	
Aim 3 (Activation)	Activation	Decision Making Involvement Scale 31‡	AYAs and Caregivers
		Survey of Caring for Children with Cancer (SCCC) †‡	
		Patient Activation Measure (PAM-13) 120†	
		Benefit Finding 121†	
	Demographic Questionnaire	Demographic information †	AYAs and Caregivers
	COVID-19 Impact	The COVID-19 Impact Questionnaire ‡	AYAs and Caregivers
	Quality of Care Checklist	Quality of Care Checklist †	AYAs

† Included in RPCA for “run-in”

‡ Included in abbreviated RPCA surveys

The full RPCA survey will be administered at baseline and week 12 in the RCT. (**Figure 3**). In order to optimize engagement, patients in both arms of the study will be asked to complete the abbreviated Resilience in Pediatric Cancer Assessment (aRPCA) during the

prospective longitudinal follow-up period (months 6, 9, and 12). The aRPCA will assess only selected outcomes (patient outcomes of HRQOL & symptoms, parent outcomes of HRQOL, and family activation variables), as described below. For those on the non-intervention arm of the study, staff will schedule a “study check-in” visit to coordinate the aRPCA completion and thank families for their continued participation.

In both arms of the study, if any participant declines to complete the full RPCA survey and/or if participants or family members report participants are unable to complete the survey due to illness complications, staff will offer in the following order: (a) an in-person (English-speaking, interview based) survey session, and (b) abbreviated versions of the questionnaire for patients to complete. Only at follow-up timepoints and in cases where participants are too ill to provide self report in writing or interviews, staff will offer abbreviated versions of the survey for *parents* to complete as proxy respondents. These options will be offered in an effort to collect full data for primary endpoint assessment, including the aRPCA or even a survey containing only the primary outcome of HRQOL.

Participants in both arms of the study will be scheduled for their surveys at the time of enrollment and then reminded prior to each survey due-date. Participants will be contacted by phone, email or mail to receive their RPCA survey. If we have not received a response within a day of initial contact, participants will receive up to 4 follow-up phone calls, texts, and/or emails (approximately once weekly) within a 28 day window before and after surveys are due. Participants will remain eligible for subsequent survey completion and follow-up even if surveys are missing and the same procedures will be conducted for each survey due-date until the 12-month follow-up point.

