recurrent cancer 2-months ahead of schedule. At the time of enrollment, 27 patients had recurrent cancer. Enrollment rates were 78% and similar among patients with new versus recurrent cancer. Thirteen experienced progressive disease during the study observation period, and 18 died of disease or treatment-related mortality prior to the 6-month end-point, including 5 of the 27 who enrolled with recurrent cancer. Attrition among surviving participants was similar on the PRISM (25%) and usual care (14%) arms, and primarily due to medical complications. Of 49 AYAs assigned to PRISM, 48 completed  $\geq 1$ , and 43 completed all scheduled sessions. Only 2 PRISM and 6 usual care patients declined continued participation due to the burden of intervention sessions or surveys.

The primary objective of the phase II RCT was to assess patient-reported resilience 6 months following enrollment. Secondary outcomes included psychological distress and HRQOL at the same time-point. Final pilot results ( $n=92$  with intention-to-treat analyses) suggest the intervention was associated with improved patient-reported resilience, distress, and quality of life scores with moderate effect sizes (**Table 2**). Exploratory analyses suggested a stronger intervention effect among AYAs who enrolled with advanced cancer (**Figure 2**). Taken together, these findings are promising because: (a) meta-analyses suggest even small effect sizes of positive psychology interventions are associated with clinically meaningful patient-centered outcomes; (b) we demonstrated feasibility among the sickest patients with advanced cancer; and, (c) the intervention may be even more impactful in this high risk group of patients.

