All of the sessions of the PRISM will be audio-recorded as possible, barring issues with the recorder or refusal of the patient to be recorded. Sessions will not be recorded through WebEx, Zoom, or Skype platforms. Administrators of PRISM will explain that the sessions will be taped and reviewed by the study team with the goal of assessing adherence to the protocol, inclusion of required elements, and presence/absence of additional information with the exception of the feedback questions. As possible, the PI or supervising team member will review the first 6 sessions for each interventionist, and score them for fidelity using a standardized tool (see appendix). After the first 6 sessions are reviewed for each interventionist, approx. one in every 5 sessions will be randomly selected to be monitored for fidelity, with feedback and re-training regarding adherence to protocol and approach to be refined if needed.

Participants on the intervention arm will also receive once every other week “booster” contacts until they reach the 3 month point from enrollment, for both the run in and the RCT. These will include brief (10-20 minute) in-person contacts in clinic, in the hospital, via phone or other web

based communication (Zoom, WebEx, or Skype) or by email and will consist of opportunities to practice specific skills (at the patient's discretion). Study staff will contact patients to coordinate such visits and will prompt them by asking: "Would you like to review or practice any of the resilience skills?" [If needed, staff will remind patients of all 5 sessions. If patients are willing, study staff will ask,] "Which one?"

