### 11.5.3 Secondary Outcomes

**11.5.3.1** The goal for parent outcomes is to evaluate the effect of the intervention on *parent psychological distress* and HRQOL. Mean total scores from each parent instrument at 12 weeks will be the secondary outcomes of interest. We will model distress and HRQOL separately and follow a similar approach to the analyses for continuous outcome measures in Aim 1. As sex and baseline patient HRQOL may be predictors of these outcomes, each will be included if imbalanced between arms.

**11.5.3.2** To compare patient and caregiver *activation*, we will measure patterns in multiple domains: AYA- and parent-reported Decision-Making Involvement Scores, AYA participation in goals of care conversations, and formal palliative care service utilization including documented referrals for hospice and charted decisions to limit resuscitative efforts. For all outcomes, results between trial groups will be compared using analysis of variance with trial group as the factor of interest. We will explore whether change in activation scores are correlated within families and/or modified by parent/child characteristics (sex, psychological distress scores, cancer/tumor-type, among others) using ordinal logistic regression models with cumulative logits, where change activation level is categorized as negative, null, or positive.

**11.5.3.3 Exploratory analyses** will evaluate prospective and longitudinal survey and clinical data beyond month 3 (primary endpoint) at months 6, 9, and 12 of the study. Comparisons between groups will still use an intention to treat approach as described above. Additionally, we will explore the relationship between biomedical variables and patient reported anxiety and depression through a combination of paired and unpaired t-tests, chi-squared (or Fisher's exact) tests, and linear and logistics regression. HRV will be measured in 24-hour increments using both time and frequency domain parameters as established by the international Cardiology task force

guidelines. Means and standard deviations will be compared to published normative data in adolescents.

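### At months 6, 9 and 12 the text schedules a survey check-in visit for the control arm only, so survey contact differs by arm in the exploratory longitudinal comparison

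*Combined protocol and SAP*

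**What the plan says.** Section 9.6 (text around Table 5) collects the full survey at baseline and week 12, and the abbreviated version (aRPCA) from both arms at months 6, 9 and 12.

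The common procedures are stated clearly. "Participants in both arms of the study will be scheduled for their surveys at the time of enrollment and then reminded" before each due date; non-responders get up to four further contacts; and "the same procedures will be conducted for each survey due-date until the 12-month follow-up point".

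The paragraph on the abbreviated survey adds one arm-specific step: "For those on the non-intervention arm of the study, staff will schedule a “study check-in” visit to coordinate the aRPCA completion". The visit is also meant to thank families. Its mode is not given.

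On the PRISM side, Section 9.4 provides fortnightly booster "contacts until they reach the 3 month point from enrollment, for both the run in and the RCT". No later PRISM contact is described.

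Section 15.0 states that staff and participants are unblinded once randomized. Section 1.2.3.6 lists the later time points as an aim to explore, and Section 11.5.3.3 places them under exploratory analyses, adding: "Comparisons between groups will still use an intention to treat approach as described above".

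**The concern.** In a comparison of self-reported outcomes, the effort made to obtain the outcome should not depend on the arm. Here one arm has an extra scheduled contact whose stated purpose is to get the survey done. That could act in two ways. It could raise control-arm completion, so that the two sets of respondents are selected differently. It is also additional study attention, in a trial of a supportive intervention delivered through contact with study staff.

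Intention-to-treat analysis keeps participants in their assigned arms but does not equalise how their outcomes are obtained. At stake is the interpretation of durability, which Section 1.3 gives as the reason for quarterly follow-up over a year.

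**Working it through.** **1. The plan's own figures, to fix the scope.** Section 11.3.1.1 and Table 7 use SD 17.2, 72 evaluable per arm, 5% type I error and 80% power. With a two-sided t-test (sidedness is not stated), the detectable difference is 8.09 points and the power for 8.1 points is 80.1%. Inflating for 26% attrition gives 144 / 0.74 = 194.6, so 195. These reproduce the stated 8.1 and 195. They concern the 3-month score from the full survey, and the check-in plays no part in them.

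**2. Contact by arm at months 6, 9 and 12, as the text has it.**

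| Contact | PRISM | Usual care | Source |
|---|---|---|---|
| Surveys scheduled at enrollment | yes | yes | 9.6 |
| Reminder before each due date | yes | yes | 9.6 |
| Up to four follow-up contacts | yes | yes | 9.6 |
| Booster contacts | ended at month 3 | none | 9.4 |
| Check-in visit for the aRPCA | not described | yes | 9.6 |

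The arms differ in one row, and the boosters cannot offset it because they have stopped by then.

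**3. How large could an effect be?** The documents do not give the inputs, so this is an illustration only. Let *r* be the response rate without the visit, *e* the completion the visit adds in controls, and *g* the PedsQL gap between the added responders and the other responders. The control respondents' mean then moves by

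shift = *g* × *e* / (*r* + *e*)

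Assumed ranges: *r* = 0.74 (one minus the planned 26% attrition) down to 0.60; *e* = 0.05 to 0.15; *g* = 5 points up to one SD, 17.2.

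| *r* | *e* | *g* | Shift (points) |
|---|---|---|---|
| 0.74 | 0.05 | 5 | 0.25 / 0.79 = 0.32 |
| 0.74 | 0.10 | 10 | 1.00 / 0.84 = 1.19 |
| 0.74 | 0.15 | 17.2 | 2.58 / 0.89 = 2.90 |
| 0.60 | 0.05 | 5 | 0.25 / 0.65 = 0.38 |
| 0.60 | 0.10 | 10 | 1.00 / 0.70 = 1.43 |
| 0.60 | 0.15 | 17.2 | 2.58 / 0.75 = 3.44 |

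The range is about 0.3 to 3.4 points, against the 4.4 listed in Table 7 as the minimal clinically important difference.

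**4. Sign.** The formula gives a size, not a direction. If the added controls are sicker, the control mean falls and PRISM looks better; if they are healthier, the reverse. An attention effect that raised control scores would work against PRISM. A shift is also not bias in itself: retaining sicker controls brings the control mean closer to that of the whole arm. Any bias comes from retaining such participants in one arm and not in the other.

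**The case against.** Much of the opposing case stands.

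- **Scope.** The comparison is exploratory, and the difference is one added contact on a shared base of scheduling, reminders and chasing.
- **Silence is not proof.** Section 9.5.1 refers to Figure 3B for the RCT survey schedule, and that figure is not shown in the text available to me. It may list a PRISM contact. The written protocol does not.
- **Safeguards.** Section 11.5.3.6 plans to quantify missing data, relate it to participant characteristics, use multiple imputation or weighting, and run sensitivity analyses for data missing not at random. Section 11.5.2 puts response type into sensitivity analyses, in text written for the primary and AYA secondary outcomes. These help with unequal response. They do not equalise contact or remove an attention effect from completed surveys.

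A reader might infer more than the documents support, in three ways.

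- **That the visit widens an existing retention gap in favour of controls.** Section 2.1.2.6 reports of the phase II trial: "Attrition among surviving participants was similar on the PRISM (25%) and usual care (14%) arms". That is an 11-point difference, but the authors call it similar and attribute attrition mainly to medical complications, which a check-in would not obviously prevent. In the same trial, 2 PRISM and 6 usual-care patients stopped because of burden, so on that kind of dropout controls did worse.
- **That the visit produces an apparent PRISM benefit.** This needs an assumed gain in completion, an assumed score gap and a chosen sign, and it leaves out attention effects that could run the other way.
- **That control surveys will more often be completed in person.** Section 9.6 gives no mode for the check-in, and it offers in-person interviews in both arms when needed.

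**Conclusion.** The point holds as a minor one. As written, the protocol makes survey contact at months 6, 9 and 12 depend on a known allocation, and nothing in the text balances it. Response and study attention may differ by arm as a consequence, but that is an inference; the documents report no effect of such a visit.

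The size and direction of any bias cannot be determined from the documents. The 0.3 to 3.4 point range rests wholly on assumed response rates, completion gains and score gaps, and should be read as applying in either direction. The 3-month primary analysis, its sample size and its power are untouched. The conclusion also assumes that Figure 3B does not schedule an equivalent PRISM contact; if it does, the remedy is only to make the text agree with it.

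**What to change.** Amend the sentence in Section 9.6 so that survey contact at months 6, 9 and 12 is the same in both arms. Either:

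- offer PRISM participants the identical check-in, with the same script, mode and timing; or
- drop the check-in and rely on the scheduling, reminders and follow-up contacts already common to both arms.

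In addition, state in Section 11.5.3.3 that response rate and mode of completion will be reported by arm at each of the three time points.

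Cost: extending the check-in adds a brief contact at three time points, at most 98 × 3 = 294 contacts if all 98 planned PRISM participants remain in follow-up. Section 28.1 already aims to combine study visits with medical visits. Dropping it costs no staff time but may lose some control-arm surveys.

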### 9.6.1 RPCA item details

#### 9.6.1.1 AYA Version (not included in parent surveys):

**9.6.1.1.1 Pediatric Quality of Life (PedsQL) Generic and Cancer Module Teen Reports.** The PedsQL 4.0 Generic and 3.0 Cancer Module include 50 items evaluating HRQOL of AYAs with cancer. Queries assess physical, emotional, social, and school well-being, plus cancer-related pain and hurt, nausea, procedural anxiety, treatment anxiety, worry, cognitive problems, perceived physical appearance, and communication. Scales are available for teens and young adults, and have been used successfully with low rates of refusal and minimal missing data. Items are rated on a 5-point Likert scale and total scores transformed to a 0-100 scale with higher scores representing better HRQOL. Internal consistency ranges from 0.75 to 0.92. These instruments are included in all surveys, including the full surveys for the run-in Cohort and RCT, and the abbreviated survey for the RCT.

**9.6.1.1.2 Hospital Anxiety and Depression Scale (HADS).** The HADS assesses mixed affective symptoms in patients with serious illness. It has been validated in AYAs with chronic illness as well as AYA cancer survivors. The scale has excellent reliability ( $\alpha=0.83-0.82$ ). It consists of 7 questions for anxiety and 7 for depression. Each is scored from 0-3, for a total range of 0-21 points per subscale. “Caseness” of anxiety and depression is defined as  $\geq 8$  points, with sensitivity/specificity of 0.8/0.9 for anxiety and 0.8/0.8 for depression. This

instrument will be included only in PARTICIPANT surveys. It will be included in both full and abbreviated surveys (RPCA and aRPCA) in order to optimize primary outcome data collection in the event of illness complications or death.

**9.6.1.1.3 Memorial Symptom Assessment Scale (MSAS).** The MSAS measures the presence, severity, frequency, and extent of bother from symptoms with high consistency ( $\alpha>0.8$ ). For the run-in, we will use the Pediatric-validated MSAS instrument (32-items) and for the RCT, we will use a version of the MSAS that has been previously developed for and used among children with advanced cancer (26-items Likert scales assess physical (pain, fatigue, drowsiness, nausea, anorexia, cough, diarrhea, vomiting, itching, skin issues, constipation, dysphagia, dry mouth, numbness, sweating, dyspnea, and dysuria), and psychological (irritability, sleep disturbance, nervousness, sadness, worrying, difficulty concentrating, and image issues) symptoms. Total- and sub-scores are calculated as an average, with higher scores representing higher symptom burden. This instrument is included in all surveys, including the full surveys for the run-in Cohort and RCT, and the abbreviated survey for the RCT

**9.6.1.1.4 Hope Scale.** The Snyder “Hope” Scale contains 8 hope items plus 4 “filler” questions, and measures “the overall perception that one’s goals can be met.” The instrument was named based on patterns of hopeful thought and assesses patient-reported efficacy by assessing the ability to generate a route to one’s goals (termed “pathway” thoughts) and the ability to initiate and maintain the actions necessary to reach a goal (termed “agency” thoughts). Prior studies performed among AYA cancer patients have shown that high-hope individuals have improved psychosocial outcomes. The instrument has been validated in both adult and pediatric settings and is scored on an 8-point Likert scale. Higher scores imply greater levels of hopeful thought patterns. Cronbach’s alphas for the whole scale range from .74 to 0.84. This instrument is included in the full (not abbreviated) surveys for both the run-in cohort and the RCT.

**9.6.1.1.5 Connor-Davidson Resilience Scale.** The Connor-Davidson Resilience Scale is a reliable and widely used instrument to measure inherent resiliency. Questions revolve around personal problem-solving and approaches to adversity. The 10-item instrument has high internal consistency (Cronbach’s alpha = 0.85), and has been used in diverse populations including adolescents, parents and cancer patients. Correlative studies have evaluated the scale with other psychosocial measures such as psychological distress, PTSD, and social support. It also has been used in pharmacologic and other intervention studies to model modifiable outcomes. Each item consists of a 5-point Likert scale (scored from zero to four) for total of 40 points. The mean score among well US adults is 31.8, with higher scores reflecting greater resilience. This instrument is included in the full (not abbreviated) surveys for both the run-in cohort and the RCT.

**9.6.1.1.6 Patient Activation Measure.** The 13-item PAM includes 3 domains to measure AYA or parent knowledge, confidence, and willingness to act regarding the AYA’s health. It is well-validated among chronically ill and healthy

adult populations, and studied among AYAs and parents of children with cancer. Both patient and parent versions have acceptable internal consistency and reliability ( $\alpha=0.86$  and 0.85, respectively). Items are scored on a 4 point Likert scale; responses are summed and transformed to 0-100. Higher scores suggest higher activation and thresholds distinguish 4 categories: (1) staying the course; (2) taking action; (3) confidence and knowledge to take action; and (4) believes active role important. This survey is only included in the run in.

**9.6.1.1.7 Benefit/Burden Scale for Children:** The Benefit/Burden Scale for Children (BBSC) was adapted by pediatric psychosocial clinicians from the Benefit Finding Scale for Children. BBSC measures benefit finding, illness-perceived burdens and psychological functioning in children. Factor analysis revealed a two-factor solution and each subscale had strong internal validity; benefit finding ( $\alpha = .852$ ; 10 items) and illness-related burden ( $\alpha = .804$ ; 10 items). All items are answered on a 5-point Likert scale ranging from “not at all” to “very much.” This survey is only included in the run in.

**9.6.1.1.8 Quality of Care.** The run in will include a check list asking AYAs about quality of care from their care team.

